Dryness **Fatigue** **Pain** **Mental Fatigue**

/ / / / / / / /

13. *Among the following dryness symptoms, please identify the one you consider the **most** in need for improvement (**tick only one box**)

Ocular **Oral** **Skin** **Nasal** **Tracheal** **Vaginal**

14. *Among the following dryness symptoms, please rank them by priority order: - from **1**: the **most** in need of improvement → to **6**: the **least** in need of improvement.

Ocular **Oral** **Skin** **Nasal** **Tracheal** **Vaginal**

/ / / / / / / / / / / /

15. *How important is it to you to get rid of your dryness?

Not important at all Extremely important
0 1 2 3 4 5 6 7 8 9 10

16. *How important is it to you to get rid of your fatigue?

Not important at all Extremely important
0 1 2 3 4 5 6 7 8 9 10

17. *How important is it to you to get rid of your pain?

Not important at all		Extremely important									
	0	1	2	3	4	5	6	7	8	9	

18. *How important is it to you to get rid of your mental fatigue?

Not important at all		Extremely important									
	0	1	2	3	4	5	6	7	8	9	

19. *Considering now your symptoms related to your Sjögren's syndrome (e.g., dryness, your fatigue, pain and your mental fatigue), as well as their consequences on your professional or personal life, how severe was your Sjögren's syndrome during the last 2 weeks?

Inactive disease		Very active disease									
	0	1	2	3	4	5	6	7	8	9	

20. *How long has it taken you to complete this questionnaire?

_____ minutes

21. *How easy or difficult have you found it to complete this questionnaire?

Very easy		Very difficult									
	0	1	2	3	4	5	6	7	8	9	

Comments

18 Appendix 6: Blinding and unblinding

Randomization data are kept strictly confidential, and are accessible only to authorized personnel, until unblinding of the trial as described in the table below.

Table 18-1 Blinding levels Cohorts 1 and 2

Role	Time or Event						
	1	2	3	4	5	6	7
Drug Supply	UI	UI	UI	UI	UI	UI	UI
Randomization Office	UI	UI	UI	UI	UI	UI	UI
Investigational site unblinded pharmacist	UI	UI	UI	UI	UI	UI	UI
Subject	B	B	B	UI	B	B	UI
Treating Physician	B	B	B	UI	B	B	UI
Primary Investigator	B	B	B	UI	B	B	UI
Unblinded Physician for safety monitoring ¹	B	B	UI	UI	UI	UI	UI
Study Monitor	B	B	B	UI	B	B	UI
Clinical Trial Leader	B	B	B	UI	UI	UG	UI
Data Manager	B	B	B	UI	B	B	UI
PK Bioanalytics	B	UI	UI	UI	UI	UI	UI
PK Expert	B	B	B	UI	UI	UG	UI
Statistician	B	B	B	UI	UI	UI	UI
Translational Medicine Expert	B	B	B	UI	UI	UG	UI
Modeler	B	B	B	UI	UI	UI	UI
Programmer	B	B	B	UI	UI	UI	UI
Novartis decision teams	B	B	B	UI	UG	UG	UI

¹Note that although the unblinded physician for safety monitoring is permitted to be unblinded, (s)he will not be provided with the randomization list until the interim analysis, in order to prevent accidental unblinding of other investigational site staff.

UG Allowed to be unblinded on treatment group level

UI Allowed to be unblinded on individual patient level

B Remains blinded

1 Generation of randomization list, QC and lock randomization list

2 Patient allocation to treatment

3 Treatment administration

4 Safety emergency event (unblinding of a single subject)

5 Interim analysis (all patients included in the analysis have completed the study)

6 Interim analysis (some patients included in the analysis have not yet completed the study)

7 Database lock

Table 18-2 Blinding levels Cohort 3

Role	Time or Event						
	1	2	3	4	5	6	7
Drug Supply	UI	UI	UI	UI	UI	UI	UI
Randomization Office	UI	UI	UI	UI	UI	UI	UI
Investigational site unblinded pharmacist	UI	UI	UI	UI	UI	UI	UI
Subject	B	B	UI	UI	UI	UI	UI
Treating Physician	B	B	UI	UI	UI	UI	UI
Primary Investigator	B	B	UI	UI	UI	UI	UI
Unblinded Physician for safety monitoring ¹	B	B	UI	UI	UI	UI	UI
Study Monitor	B	B	UI	UI	UI	UI	UI
Clinical Trial Leader	B	B	UI	UI	UI	UI	UI
Data Manager	B	B	UI	UI	UI	UI	UI
PK Bioanalytics	B	UI	UI	UI	UI	UI	UI
PK Expert	B	B	UI	UI	UI	UI	UI
Statistician	B	B	UI	UI	UI	UI	UI
Translational Medicine Expert	B	B	UI	UI	UI	UI	UI
Modeler	B	B	UI	UI	UI	UI	UI
Programmer	B	B	UI	UI	UI	UI	UI
Novartis decision teams	B	B	UI	UI	UI	UI	UI

¹Note that although the unblinded physician for safety monitoring is permitted to be unblinded, (s)he will not be provided with the randomization list until the interim analysis, in order to prevent accidental unblinding of other investigational site staff.

- UG Allowed to be unblinded on treatment group level
- UI Allowed to be unblinded on individual patient level
- B Remains blinded
- 1 Generation of randomization list, QC and lock randomization list
- 2 Patient allocation to treatment
- 3 Treatment administration
- 4 Safety emergency event (unblinding of a single subject)
- 5 Interim analysis (all patients included in the analysis have completed the study)
- 6 Interim analysis (some patients included in the analysis have not yet completed the study)
- 7 Database lock

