7.2 Serious adverse event reporting

To ensure subject safety, every SAE, regardless of causality, occurring after the subject has provided informed consent and until 30 days after the last study visit must be reported to Novartis within 24 hours of learning of its occurrence. Any SAEs experienced after the 30 days period should only be reported to Novartis if the investigator suspects a causal relationship to study treatment.

Recurrent episodes, complications, or progression of the initial SAE must be reported as follow-up to the original episode, regardless of when the event occurs. This report must be submitted within 24 hours of the investigator receiving the follow-up information. An SAE that is considered completely unrelated to a previously reported one should be reported separately as a new event.

Information about all SAEs (either initial or follow up information) is collected and recorded on the paper Serious Adverse Event Report Form. The investigator must assess the relationship to study treatment complete the SAE Report Form in English, and send the completed, signed form by fax within 24 hours after awareness of the SAE to the local Novartis Drug Safety and Epidemiology Department. The telephone and fax number of the contact persons in the local department of Drug Safety and Epidemiology, specific to the site, are listed in the investigator folder provided to each site. The original copy of the SAE Report Form and the fax confirmation sheet must be kept with the case report form documentation at the study site. Follow-up information should be provided using a new paper SAE Report Form stating that this is a follow-up to a previously reported SAE.

Follow-up information provided should describe whether the event has resolved or continues, if and how it was treated, whether the treatment code was broken or not and whether the subject continued or withdrew from study participation. Each re-occurrence, complication, or progression of the original event should be reported as a follow-up to that event regardless of when it occurs.

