7.3 Liver safety monitoring

To ensure subject safety and enhance reliability in determining the hepatotoxic potential of an investigational drug, a standardized process for identification, monitoring and evaluation of liver events has to be followed.

Liver events are divided into two categories:

- Liver events of special interest (AESI) which consist of elevated liver function tests LFTs.

- Medically significant liver events which are considered as serious adverse events (SAEs) and which consist of marked elevations of LFTs.

Please refer to [Table 15-1-Appendix 3](#) for complete definitions of liver events.

Any liver event which meets the criteria for a “**medically significant**” event should follow the **standard procedures for SAE reporting** as described in [Section 7.2](#).

Every liver event as defined in [Table 15-1-Appendix 3](#) should be followed up by the investigator or designated personnel at the trial site, as summarized below and detailed in [Table 15-2-Appendix 3](#).

- Repeating the LFT to confirm elevation as appropriate
- Discontinuation of the investigational drug if appropriate
- Hospitalization of the subject if appropriate
- A causality assessment of the liver event via exclusion of alternative causes (e.g., disease, co-medications)
- An investigation of the liver event which needs to be followed until resolution.

These investigations can include serology tests, imaging and pathology assessments, hepatologist’s consultancy, based on investigator’s discretion. All follow-up information, and the procedures performed should be recorded as appropriate in the eCRF.

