
Youinou P, Pers JO (2012) Latest update on the primary Sjögren's syndrome. *Presse Med*; 41 (9 pt 2):e437-439.

Corporate Confidential Information

14 Appendix 2: Sample labeling and shipping information

Sample labeling and shipping instructions will be provided in a separate laboratory manual.

15 Appendix 3: Liver event definitions and follow-up requirements

Table 15-1 Liver Event Definitions

	Definition/ threshold
Adverse event of special interest	
Laboratory values	ALT or AST > 3 x ULN ALP > 2 x ULN TBL > 1.5 x ULN
Medically significant event (SAE)	
Laboratory values	ALT or AST > 5 x ULN (with or without TBL > 2 x ULN [mainly conjugated fraction]) ALP > 5 x ULN (with or without TBL > 2 x ULN [mainly conjugated fraction]) TBL > 3 x ULN Potential Hy's Law cases (defined as ALT/AST > 3 x ULN and TBL > 2 x ULN [mainly conjugated fraction] without notable increase in ALP to > 2 x ULN)
Adverse events	Any clinical event of jaundice (or equivalent term) ALT or AST > 3 x ULN accompanied by general malaise, fatigue, abdominal pain, nausea, or vomiting, or rash with eosinophilia Any event that links to a preferred term (PT) in the MedDRA dictionary falling under the SMQ sub-module "Drug-related hepatic disorders – severe events only"* or any "Hy's law case" PT

*These events cover the following: hepatic failure, fibrosis and cirrhosis, and other liver damage-related conditions; the non-infectious hepatitis; the benign, malignant and unspecified liver neoplasms.

Table 15-2 Liver Event Follow Up Requirements

Criteria	Event type	Actions required	Follow-up monitoring
Potential Hy's Law case ^a	Medically significant	Discontinue the study drug immediately Hospitalize, if clinically appropriate Report to Novartis as an SAE Establish causality	ALT, AST, TBL, Alb, PT, ALP and γ GT until resolution ^c (frequency at investigator discretion)
ALT or AST			
> 8 x ULN	Medically significant	Repeat LFT within 48 hours If elevation persists, discontinue the study drug immediately Hospitalize if clinically appropriate Report to Novartis as an SAE Establish causality	ALT, AST, TBL, Alb, PT, ALP and γ GT until resolution ^c (frequency at investigator discretion)

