> 5 to \leq 8 x ULN	Medically significant	Repeat LFT within 48 hours If elevation persists for more than 2 weeks , discontinue the study drug Report to Novartis as an SAE Establish causality	ALT, AST, TBL, Alb, PT, ALP and γ GT until resolution ^c (frequency at investigator discretion)
> 3 x ULN accompanied by symptoms ^b	Medically significant	Discontinue the study drug immediately Hospitalize if clinically appropriate Report to Novartis as an SAE Establish causality	ALT, AST, TBL, Alb, PT, ALP and γ GT until resolution ^c (frequency at investigator discretion)
> 3 to \leq 5 x ULN (patient is asymptomatic)	AESI	Central laboratory to report to Investigator & Novartis Repeat LFT once or twice in the week If elevation persists, establish causality	Investigator discretion Monitor LFT within 1 to 4 weeks or at next visit
\leq 3 x ULN (patient is asymptomatic)	N/A	Repeat LFT at next visit	
ALP (isolated)			
> 5 x ULN	Medically significant	Repeat LFT within 48 hours If elevation persists, report to Novartis as an SAE Establish causality	Investigator discretion Monitor LFT within 1 to 4 weeks or at next visit

Criteria	Event type	Actions required	Follow-up monitoring
> 2 to ≤ 5 x ULN (patient is asymptomatic)	AESI	Central laboratory to report to Investigator & Novartis Repeat LFT once or twice in the weekIf elevation persists, establish causality	Investigator discretion Monitor LFT within 1 to 4 weeks or at next visit
≤ 2 x ULN (patient is asymptomatic)	N/A	Repeat LFT at next visit	
TBL (isolated)			
> 3 x ULN	Medically significant	Repeat LFT within 48 hours If elevation persists, discontinue the study drug immediately Hospitalize if clinically appropriate Report to Novartis as an SAE Establish causality	ALT, AST, TBL, Alb, PT, ALP and γGT until resolution ^c (frequency at investigator discretion) Test for hemolysis (e.g., reticulocytes, haptoglobin, unconjugated [indirect] bilirubin)
> 1.5 to ≤ 3 x ULN (patient is asymptomatic)	AESI	Central laboratory to report to Novartis Repeat LFT once or twice in the weekIf elevation persists, establish causality	investigator discretion Monitor LFT within 1 to 4 weeks or at next visit
≤ 1.5 x ULN (patient is asymptomatic)	N/A	Repeat LFT at next visit	
Preferred terms			
Jaundice	Medically significant	Discontinue the study drug immediately Hospitalize the patient Report to Novartis as an SAE Establish causality	ALT, AST, TBL, Alb, PT, ALP and γGT until resolution ^c (frequency at investigator discretion)

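### Table 15-2 makes the SAE report of isolated ALP above 5 x ULN depend on a persisting elevation, while Table 15-1 and Sections 7.3 and 7.2 require it within 24 hours without that condition

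*Protocol*

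**What the plan says.** Appendix 3 of the protocol handles liver events in two tables: Table 15-1 defines them and Table 15-2 lists the actions. Sections 7.2 and 7.3 govern reporting.

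- **Table 15-1**, under the laboratory values that make a medically significant event (SAE), lists "ALP > 5 x ULN (with or without TBL > 2 x ULN [mainly conjugated fraction" (closing brackets cut). No repeat or persistence is asked for.
- **Section 7.3** describes this category as "Medically significant liver events which are considered as serious adverse events (SAEs) and which consist of marked elevations of LFTs". It adds that any medically significant "event should follow the standard procedures for SAE reporting as described in" Section 7.2.
- **Section 7.2** says that every SAE, whatever its cause, "must be reported to Novartis within 24 hours of learning of its occurrence".
- **Table 15-2**, in the row for isolated ALP above 5 x ULN, also labels the event medically significant, but gives the action as "Repeat LFT within 48 hours If elevation persists, report to Novartis as an SAE".

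**The concern.** The same laboratory value is an SAE on first observation in one table, and is reported as an SAE only after confirmation in the other. Section 7.3 points sites to Table 15-2 for the detailed steps, so a site acting in good faith can follow the conditional row and miss the 24-hour duty.

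What is at stake is the completeness and timing of SAE reports. One stopping rule in Section 5.5.10 counts subjects with treatment-related SAEs, and Section 8.4 says that no data monitoring committee is required. A drug-related ALP event that never gets an SAE report could therefore be left out of that count.

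**Working it through.** No figure in the plan needs to be reproduced. The check compares the texts and then works out the timing.

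**1. Do both tables cover the same event?** Yes. Table 15-1 covers ALP above 5 x ULN with or without raised bilirubin, so an isolated rise is included. Table 15-2 gives its isolated-ALP row the same label, medically significant.

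**2. Does the condition really govern the report?** Table 15-2 has 8 rows labelled medically significant:

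| Row | What depends on persistence | SAE report |
|---|---|---|
| Potential Hy's Law | nothing | unconditional |
| ALT/AST > 8 x ULN | stopping the drug | separate item |
| ALT/AST > 5 to ≤ 8 x ULN | stopping the drug (more than 2 weeks) | separate item |
| ALT/AST > 3 x ULN with symptoms | nothing | unconditional |
| ALP > 5 x ULN (isolated) | **the SAE report** | **conditional** |
| TBL > 3 x ULN (isolated) | stopping the drug | separate item |
| Jaundice | nothing | unconditional |
| Severe hepatic disorders SMQ | nothing | unconditional |

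The line breaks inside the cells are lost in the available text, but capitalisation separates the items. In the > 5 to ≤ 8 row the text runs "discontinue the study drug Report to Novartis as an SAE", where the capital letter opens a new action. In the ALP row the verb is lower case and completes the conditional sentence. So 1 row of 8 makes the report itself conditional, and 7 do not.

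**3. Timing.** Let the first result be known at hour 0 and the repeat at hour t, with t ≤ 48. The limit is 24 hours. Laboratory turnaround is not counted.

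- Report sent when the repeat is known: lateness = max(0, t − 24). At t = 48 this is 48 − 24 = 24 hours. At t ≤ 24 it is 0.
- Site starts a new 24-hour clock at the repeat: greatest lateness = t + 24 − 24 = t. At t = 48 this is 48 hours; at t = 24 it is 24 hours.
- ALP no longer elevated on repeat: the row calls for no SAE report at any time.

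**4. Example.** For an isolated ALP of 6 x ULN, Table 15-1 with Sections 7.3 and 7.2 gives an SAE report by hour 24. The Table 15-2 row gives a repeat by hour 48, and a report only if the rise persists.

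**The case against.** The best case for the plan has four parts.

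- **Section 7.3 already says what governs.** It assigns SAE reporting to Section 7.2 and cites Table 15-2 for follow-up only. This shows which text ought to win. But Table 15-2 carries its own reporting instruction, so the contrary wording is still in front of the site.
- **A confirmatory repeat is allowed for.** Section 7.3 does list it, but as a follow-up step where appropriate. Nothing there suspends the 24-hour duty.
- **Lighter handling may be intended.** The isolated-ALP row also leaves out stopping the drug and hospitalization. If the sponsor wanted confirmation first, however, Table 15-1 and Section 7.3 would have to say so, and they do not.
- **The sponsor may hear anyway.** Section 6.5.4 requires clinically relevant laboratory deviations to be raised with the sponsor and repeated until resolved. This stands. A reader might infer that transient ALP rises would be hidden from the sponsor altogether, and the documents do not support that. What can be missed is the SAE report and its deadline.

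A reader might also infer that the ALT/AST rows contradict each other. The row "> 3 x ULN accompanied by symptoms" has no upper limit and says "Discontinue the study drug immediately Hospitalize if clinically appropriate Report to Novartis as an SAE", while the two rows above 5 x ULN require a stop only on persistence. The documents do not support a conflict there. A symptomatic patient above 5 x ULN meets two separate Table 15-1 entries, one under laboratory values and one under adverse events, and Section 7.3 requires follow-up of every listed event. The symptom row's stop is unconditional, no other row tells the site to keep dosing, and all three rows call for an SAE report. They can all be obeyed together; a precedence sentence would only clarify.

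**Conclusion.** The inconsistency is real, limited to isolated ALP above 5 x ULN, and minor. Following the Table 15-2 row leads to no SAE report when the rise falls on repeat. For a persisting rise the report can be up to about 24 hours late, or 48 hours if the clock is restarted.

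These delays are upper cases. They assume that awareness begins with the first result and that the whole repeat window is used; a site that repeats and reports within 24 hours is on time. The documents give no rate of liver events, so no number of patients can be attached. Sample size, alpha and the ESSDAI analysis are unaffected.

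**What to change.** In Table 15-2, in the row for ALP above 5 x ULN, remove the persistence condition so that the SAE report stands as its own item, as in the other seven medically significant rows. Keep the repeat test within 48 hours as follow-up. This brings the row into line with Table 15-1 and Sections 7.3 and 7.2, which need no change.

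The cost is one replaced sentence in an amendment, with no added tests or visits. There may be a few more SAE reports for transient ALP rises, all of them already required by Table 15-1 and Section 7.3.

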## 1 Introduction to RAP documentation

### 1.1 Scope

The RAP documents contain detailed information to aid the production of Statistics & Programming input into the Clinical Study Report (CSR) for trial “**CCFZ533X2203**”.

**Module 3 (M3) provides the description of the statistical methodology** used to analyze the data, **Module 7 (M7)** details the presentation of the data, including shells of summary tables, figures and listings, and **Module 8 (M8)** contains programming specifications e.g. for derived variables and derived datasets, to support the creation of CSR outputs.

### 1.2 Changes to RAP documentation (M3)

Refer to corresponding guidances and Translational Sciences (TSc) RAP Addendum template for detailed information on the requirements of documenting changes to RAP documentation.

**For the statistical methodology (M3)**, any major changes occurring before database lock to the statistical methodology should be reflected in the RAP M3 documentation via version control (new document version to be approved by the trial team as the original module).

Major changes include, but are not limited to, changes in protocol that affect study design and statistical methodology.

Minor changes to the RAP M3 documentation can be captured e.g. by a study note to file / note in RAP Addendum or within the CSR itself. Minor changes include, but are not limited to, change in statistical model. Corrections of typographical errors or modification of spelling (from English to American, for example) do not need to be incorporated into the RAP M3 documentation.

## **2 Study objectives and design**

### **2.1 Study objectives**

#### **2.1.1 Primary objectives**

- To assess the safety and tolerability of multiple subcutaneous doses and multiple intravenous infusion of CFZ533 in patients with primary Sjögren's syndrome (pSS) as measured by adverse events (AEs).
- To compare the effect of multiple intravenous infusion of CFZ533 versus placebo on the clinical disease activity of pSS patients as measured by the change of an EULAR Sjögren's Syndrome Disease Activity Index (ESSDAI) after 12 weeks treatment.

#### **2.1.2 Secondary objectives**

- To assess the safety and tolerability of multiple subcutaneous doses of CFZ533 in patients with pSS as measured by AEs.
- To compare the effect of multiple subcutaneous doses of CFZ533 versus placebo on the clinical disease activity of pSS patients as measured by the change of an ESSDAI after 12 weeks treatment.
- To assess the pharmacokinetics of multiple subcutaneous doses and multiple intravenous infusion of CFZ533 in pSS patients.
- To evaluate the effect of multiple subcutaneous doses and multiple intravenous infusions of CFZ533 versus placebo on self-reported outcomes in pSS patients after 12 weeks treatment as measured by the EULAR Sjögren's Syndrome Patient Reported Intensity (ESSPRI), the Short Form (36) Health Survey (SF-36) and the Multidimensional Fatigue Inventory (MFI) Questionnaire.
- To evaluate the changes in the physician global assessment of the patient's overall disease activity as recorded by a visual analog scale (VAS) after 12 weeks treatment.
- To evaluate the changes in the patients global assessment of their disease activity as recorded by a VAS after 12 weeks treatment.

Corporate Confidential Information

## 2.2 Study design and treatment

This is a double-blind followed by open-label, randomized, placebo-controlled, parallel-group, non-confirmatory study to assess the safety, tolerability, pharmacokinetics, and preliminary clinical efficacy of multiple doses of CFZ533 in the following Cohorts 1 and 2:

- Cohort 1: CFZ533 administered subcutaneously in patients with pSS, in a doubleblind and placebo-controlled fashion, followed by open-label treatment;
- Cohort 2: CFZ533 administered by intravenous infusion in patients with pSS, in a double-blind and placebo-controlled fashion, followed by open label treatment.

These cohorts will be followed by an open label, randomized, parallel group, non-confirmatory part of Cohort 3:

- Cohort 3 (patients with pSS):  
In treatment arm 1 CFZ533 will be given at [redacted] s.c. weekly on 4 occasions (loading regimen), followed by [redacted] s.c. weekly on 9 occasions (maintenance regimen starting on study day 29). In treatment arm 2, the loading regimen will consist of a single i.v. dose of [redacted] CFZ533 (on study day 1), followed by [redacted] s.c. weekly on 12 occasions (maintenance regimen starting on study day 8).

[figure not shown]
The study will randomize approximately 68 patients with primary Sjögren's syndrome. In Cohorts 1 and 2, the randomization will be stratified by baseline intake of oral corticosteroids (yes/no). There will be no stratification in Cohort 3.

The study comprises three periods for Cohort 1 and Cohort 2:

- 1) placebo-controlled period (from Day 1, Week 1 to completion of pre-dose assessments on Day 85, Week 13), during which 4 doses of CFZ533 or placebo will be administered on top of the standard of care therapy, (e.g., low dose corticosteroid) that is necessary to treat pSS;
- 2) open-label period (from dosing on Day 85, Week 13 to completion of assessments on Day 169, Week 25), when all patients will receive 4 doses of open-label CFZ533 treatment, and
- 3) follow-up period (Weeks 25 – 32), when patients will be followed up without study medication.

An illustration of the study design for Cohorts 1 and 2 is provided in Figure 2-1.

